# Federal Regulations

1. \* Is this a FDA regulated study?

FDA regulated research includes all clinical investigations involving a test article and a human subject(s) that has been submitted for approval to the FDA or may be submitted in the future.

Check Yes if

- the study involves an IND/IDE, abbreviated IDE, IND/IDE exemption, HUD, expanded access, or is otherwise subject to 21 CFR 56,
- the study involves a test article being administered or dispensed to subjects NOT according to a clinicians• medical judgment but rather, per the study protocol, OR
- the study does not involve a test article but intends to provide safety or efficacy data to the FDA.

Yes	O No
-----	------

1/31/24, 8:55 AM	MS4_HM20020066 - Safety and Efficacy of State-of-the-Art Exoskeleton Technology to Improve Mobility in Parkinson s Diseas
2. * Indicate the	FDA regulated product(s) this study involves:
Drug	
✓ Medica	Il Device
Biologic	
Dietary	Supplement
☐ Food/Fo	ood Additive
Color Ac	
_	
_	nic Products for Human Use (radiation producing)
U Other	
3. * Is this study	y supported by the Department of Defense (DoD):
O Yes	
No No	
4. * Check if any funding):	y of the following funding sources apply to this research (including Direct and/or Indirect
☐ Departn	ment of Education
Departn	ment of Justice
Environ	mental Protection Agency
✓ None o	f the above
ID: MS4_HM2002000	
.5	1011 0.2 11.0 (d.16) 66.4p
IRB Panel	Setup
1. * To which IR	B is this study being submitted for review?
VCU IRE	
○ WCG IR	B Commence of the commence of
○ NCI Cen	ntral IRB
Advarra	
Other IR	.B
	y transitioning to review by another IRB? Insitioning from VCU IRB to an external IRB (WCG, CIRB, Other)
0	
O Yes - tra	ansitioning from an external IRB (WCG, CIRB, Other) to VCU IRB
No or no	ot applicable
ID: MS4_HM2002000	66 View: SF2 - Review Setup
Review Se	tup
1. * Select which	h study type best describes the majority of the study. Your response will help determine which ould review this. dical Research
O Social/B	dehavioral/Education (SBE) Research
This informat	on(s) best describe the way(s) this study�s procedures will be conducted? (Select all that apply.) tion may be used by the IRB in triaging studies during an emergency. tractions / interventions with participants
contingency	possible to convert in-person activities in your study to remote if there is an approved protocol? ole to convert to remote activities
4. * Does this st	tudy involve greater than minimal risk: ) No
5. * Review type	e requested: (subject to IRB approval): ard

1/31/24, 8:55 AM  Expedited  Exempt	MS4_HM20020066 - Safety and Efficacy of State-of-the-Art Exoskeleton Technology to Improve Mobility in Parkinson so Disease
6. Is this study initiate  VCU Investiga	ed by a VCU investigator or a sponsor: ttor initiated
Sponsor or industry initiated	
The IRB has detern	nined that the selected types of anticipated individual and social benefit apply to this study
categories will app	ion is read-only to investigators, and the categories are set by the IRB during review. All ear blank until the IRB has made a determination. If a category is not checked, it does not This information may be used by the IRB in triaging studies during an emergency
	direct benefit to individual participants

ID: MS4\_HM20020066

View: SF2 - Initial Setup Complete

## Initial Setup Complete

Protocol Progress:
? INITIAL SETUP

BACKGROUND, RATIONALE & GOALS
? RESEARCH PLAN
? CONSENT PLAN
? RISKS, PRIVACY & CONFIDENTIALITY
? POPULATIONS WITH SPECIAL CONSIDERATIONS
! INSTITUTIONAL REQUIREMENTS
? DOCUMENTS

Click Continue below to go to the next section

ID: MS4 HM20020066

View: SF2 - Background, Rationale and Goals

# Background, Rationale and Goals

1. \* Describe the study's background and what is currently known from the scientific literature, including citations, or upload a citation list in document upload. Use lay language whenever possible.

The extent of disability in late stage PD limits the effectiveness of medicines and physical treatment interventions. When patients become dependent on walkers for mobility or have progressed to the point of being wheelchair or bed bound, there is essentially no evidence for interventions to support recovery, much the less maintain current function.1 Typical therapy paradigms at this stage are compensatory and focus on caregiver training with reduced patient autonomy.2,3,4 Robotic-assist gait training (RAGT) has been extensively applied as a remarkable therapeutic modality, such that it is enabling highly motivated people with devastating neurologic injuries and disorders associated with near complete motor loss to regain independent ambulation. Currently, RAGT is targeted to a highly restricted population including those with spinal cord injuries, strokes, and multiple sclerosis.5 RAGT has evolved from treadmill-based training to over ground walking by means of portable robotic exoskeletons. Further, lightweight assisted devices intended for daily wear are being developed by multiple technology companies. These devices are designed to provide a passive force to assist in mobilizing the legs and to give the additional force necessary to, for example, complete a full step, aid climbing stairs or traverse a curb. Despite the remarkable potential for this cutting-edge technology to transform the lives of people with PD and other parkinsonisms, these devices are not being adequately investigated in this population. FDA approval has not yet been obtained for these over ground exoskeleton devices in our proposed population. We are, therefore, effectively the frontrunners in advancing the use of portable exoskeletons for PD and other movement disorders.

To date, RAGT has only been investigated in PD subjects using limited treadmill-based systems and these studies have only focused on those with retained independent ambulation. One such study determined that the Hocoma Lokomat♦ treadmill-based system was safe and well tolerated in patients with Hoehn & Yahr (H&Y) stages II and III when operated 3 times per week for 30 minutes per day at 2.2 ♦ 2.5 km/h. Participants experienced improvements in Tinetti Walking, Tinetti Balance, UPDRS Part III, and Geriatric Depression Scale (GDS); however, no effect was noted on 10-meter Walking Test (10MWT) or PDQ39.6 More recent case studies reported improved FOG following Hocoma Lokomat♦ training, but these studies again were focused on treadmill-based RAGT in patients who remained independent for ambulation.7

Studies in other patient populations have demonstrated training effects with treadmill based RAGT systems that typically lack carryover upon follow-up assessment.8 In comparison to RAGT treadmill systems which can perform

walking 100% passively, the increased intensity, salience, and variability in training environments afforded by over ground exoskeleton units are anticipated to yield appreciable greater therapeutic results. Patients will be able to negotiate an environment, rather than a closed course of a treadmill system, for greater engagement with changing scenery and stimulation. We recognize the importance of patient engagement and motivation as it pertains to motor control theory and neural plasticity.9 These features are crucial in retraining or maintaining a skill such as walking. Ultimately, due to the lighter weight of these portable exoskeleton devices, patients can be expected to use the devices for regular wear outside of the therapy environment. Home use is expected to not only produce better outcomes of mobility but also provide the greatest benefit to quality of life by improving or maintaining participation in family-based and community activities.

2. \* Describe the study hypothesis and/or research questions. Use lay language whenever possible. Is the wearable exoskeleton assistive technology safe for people with debilitating movement disorders to use on a daily basis?

What is the potential efficacy of wearable exoskeleton assistive technology and will it be transformative for day to day functioning of those with debilitating movement disorders?

3. \* Describe the study's specific aims or goals. Use lay language whenever possible. Aim 1. To establish the safety of a portable exoskeleton for walking training in persons with PD.

We will measure safety as it pertains to the absence of or limited adverse events with training. We will assess via tracking of adverse events throughout training, including the number of "prevented" or "near falls" requiring physical assistance by the investigative training team.

Aim 2. To assess the efficacy of a portable exoskeleton for gait mobility and postural stability in persons with PD.

Intervention efficacy will be measured through comparative analysis of pre-, post- and durability assessments of mobility and impairment. We will assess walking capacity and benefit (and safety) to management of freezing of gait (FOG) with the Six Minute Walk Test (6MWT), and Ten-Meter Walk Test (TMWT), balance and postural stability with the Berg Balance Scale (BBS), disease severity with the Examination, part III of the Unified Parkinson so Disease Rating Scale (UPDRS), and impact on quality of life and activities of daily living, through the Parkinson so Disease Questionnaire (PDQ39) and the Parkinson so Disease Carer Questionnaire (PD-Carer). During measure of the 6MWT and TMWT, both aided by the exoskeleton and unaided (i.e. standard), additional data points will be collected through use of the APDM Mobility Lab wearable sensor system. Six sensors will be placed on specific landmarks to capture truncal and appendicular movement. Our team proposes the use of the following measures to best track proficiency of exoskeleton device use and net effect on FOG: cadence, gait cycle duration, gait speed, double support time, stance time, step duration, stride length, swing phase, toe out angle, stride length variability, arm swing velocity, arm swing range of motion, and anticipatory postural adjustment via APA duration, first step duration, and first step range of motion. These anticipatory postural adjustment measures are specific to initiation of gait, a critical event impacted by FOG. Additionally, measures of truncal sway will further strengthen our assessment of postural stability relative to dynamic walking.

At end of training, the 6MWT will be compared with and without the exoskeleton towards our goal of establishing an indication for long-term studies assessing in-home use. The 6MWT will be adminstered with standard instructions while also scoring FOG based on the criteria in the UPDRS items 3.10 (Gait) and 3.11 (Freezing of Gait) during 6MWT with and without the exoskeleton.

4. \* Describe the scientific benefit or importance of the knowledge to be gained:

We expect that mobile exoskeleton devices will provide a tremendous advancement for walking and bending assistance for people with PD and other movement disorders, permitting them to maintain a more normal lifestyle and quality of life. Portable exoskeleton devices can be expected to afford major advantages over current usage and dependence on walkers in those with advancing symptoms. For those however dependent on walkers for postural stability, the addition of an exoskeleton device will permit more effective ambulation at appreciable quicker speeds. For drastically lower cost than motorized wheelchairs, personal exoskeleton devices will circumvent or delay the need of motorized wheelchair dependence and associated deterioration and shorting of life in those with debilitating movement disorders.

While PD is itself a devastating condition, atypical forms of parkinsonism do not respond to medications and current therapies offer only modest benefits and so portable exoskeletons can provide people with these conditions new hope to maintain functional mobility. A longer term goal of this work will be to continue to modify these devices to be costumed for the individual.

- 5. \* Describe any potential for direct benefits to participants in this study: Patients may have increased mobility and/or other secondary benefits after completing the trial.
- 6. \* Describe any potential for direct social impact in this study . For example, any engagement with specific communities to respond to community-identified needs, or ways the study will strengthen the well-being of the specific communities if applicable: n/a
- 7. Upload a supporting citation list if applicable:

ID: MS4 HM20020066 View: SF2 - Study Population

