## Study Population

- 1. \* Provide the maximum number of individuals that
  - May participate in any study interaction or intervention (Including screening, consenting, and study activities)
     AND/OR
  - 2. You obtain any data/specimens about (regardless of identifiability)
  - at VCU and at other sites under the VCU IRB's oversight. See the help text for additional guidance.  $90\,$
- 2. If this is a multi-Center Project, what is the maximum anticipated number of subjects across all sites?

3. \* Provide justification for the sample size by explaining how you arrived at the expected number of participants and why this number is adequate for answering the research questions:

An overarching goal of this pilot study is to obtain estimates of the means and variances of all study measures to facilitate a power analysis for future extramurally funded clinical trials. van Belle proposed that a minimum of 12 observations should be used to calculate confidence intervals based on the t-statistic with n ◆ 1 degrees of freedom.17 This rule is based on the fact that the half-width confidence interval for the mean decreases rapidly up to n = 12, at which point the decrease is less dramatic and the half-width curve begins to asymptotically decrease. Thus, the proposed sample size of 12 per H&Y group (3 groups of H&Y) should be adequate to provide means and variance for planning of future studies.

We also expect to enroll 1 caregiver for each participant enrolled.

We proposed up to 90 participants because we included persons who signed the consent but were ineligible to participate and those that started the protocol but dropped out.

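### Aim 1 promises to establish safety, but a pilot of about 36 participants sized only for means and variances leaves per-participant risks of up to about 10% open even if no event is seen

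*Protocol*

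**What the plan says.** The aim appears in the Protocol under Background, Rationale and Goals, item 3, and again under Study Procedures, item 2: "Aim 1. To establish the safety of a portable exoskeleton for walking training in persons with PD". The criterion follows at once: "We will measure safety as it pertains to the absence of or limited adverse events with training". Adverse events are tracked throughout training, together with a count of near falls in which staff had to give physical help. No acceptable rate, comparator or definition of limited is given.

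The research question behind the aim is wider: "Is the wearable exoskeleton assistive technology safe for people with debilitating movement disorders to use on a daily basis".

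The sample size is justified under Study Population, item 3, where the form asks why the number is adequate for the research questions. The answer describes a pilot: "An overarching goal of this pilot study is to obtain estimates of the means and variances of all study measures". It cites a rule of thumb that "a minimum of 12 observations should be used to calculate confidence intervals based on the t-statistic" and concludes that "12 per H&Y group (3 groups of H&Y) should be adequate to provide means and variance for planning of future studies". Safety is not mentioned there.

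Exposure is ten sessions over five weeks, with a gait belt and two staff in support (Study Procedures, item 6). Falls and musculoskeletal injury are among the listed risks. Under Risks, Discomforts, Potential Harms and Monitoring, item 6, no pre-specified safety criteria are given, so no other part of the protocol says what degree of safety would count as acceptable.

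**The concern.** The verb in Aim 1 claims more than the design can deliver. The criterion looks to the absence or scarcity of events, but in a small sample an uncommon event is often absent even when its risk is material. The one argument offered for the sample size is about the confidence interval of a mean, and it gives no information on how large an event risk the trial could rule out.

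The consequence reaches past this trial. The protocol describes the team as among the first to use portable exoskeletons in this population, and it wants the results to support long-term studies of use at home. A safety conclusion resting on few or no observed injuries would carry into those studies with more certainty than the data hold, and it would come from supervised sessions.

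**Working it through.** **Inputs.** Participants per group: 12. Groups: 3. Both are from Study Population, item 3; the total 3 x 12 = 36 is derived. Exposure: ten supervised sessions, from Study Procedures, item 6. Confidence level: 95%, assumed because the protocol gives none; two-sided limits are primary and one-sided limits are shown beside them.

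**Step 1: the plan's own figure.** The half-width of a 95% t-interval for a mean, in standard deviations, is t(0.975, n-1)/sqrt(n).

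| n | Half-width (SD) | Gain from the last added participant |
|---|---|---|
| 6 | 1.049 | 0.192 |
| 12 | 0.635 | 0.036 |
| 20 | 0.468 | 0.014 |

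The flattening near 12 that the protocol describes is reproduced. For means, the argument does what it says.

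**Step 2: the same size applied to an event risk.** With zero events in n participants, the exact upper limit is 1 - 0.025^(1/n) two-sided, or 1 - 0.05^(1/n) one-sided.

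- n = 36, two-sided: 1 - 0.025^(1/36) = 0.0974, or 9.7%.
- n = 36, one-sided: 1 - 0.05^(1/36) = 0.0798, or 8.0%.

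**Step 3: limited rather than absent events.** Exact two-sided 95% upper limits for n = 36 are 14.5% with one participant affected and 18.7% with two.

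**Step 4: how often none would be seen.** The chance of no event in 36 participants is (1 - p)^36.

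- True risk 5%: 0.95^36 = 0.158.
- True risk 2%: 0.98^36 = 0.483.
- True risk 1%: 0.99^36 = 0.696.

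**Step 5: scale.** To exclude a risk p with zero events, n must be at least ln(0.025)/ln(1 - p) two-sided, or ln(0.05)/ln(1 - p) one-sided. For p = 5% this is 72 or 59 participants; for p = 1%, 368 or 299.

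**Step 6: if more than 36 are exposed.** The enrolment ceiling is 90, and the form explains that "We proposed up to 90 participants because we included persons who signed the consent but were ineligible to participate" or dropped out. With 45 exposed, the zero-event limit is 1 - 0.025^(1/45) = 7.9%. Even if all 90 walked in the device, which that explanation rules out, it would be 4.0%.

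**The case against.** Several points on the other side stand.

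- **No zero-event rule.** A reader might infer that a trial with no injuries would be reported as having established safety. The protocol does not say so: it states what is measured and sets no pass/fail conclusion, and the word limited allows for events. The fault is in what the aim and criterion would permit.
- **Modest purpose.** The sample-size text calls this a pilot and claims adequacy only for planning later studies, and the form asks for lay language. This makes the intention reasonable, but it also shows that the aim is worded more strongly than the design behind it.
- **Near falls are counts.** Near falls, the one safety measure Aim 1 names specifically, are counted over ten sessions. A count per participant has a mean and variance, so the sample-size argument can partly cover it. The problem is confined to uncommon harms.
- **The group figure.** A reader might lead with the limit for a single H&Y group, 1 - 0.025^(1/12) = 26.5% with no events. Aim 1 concerns people with PD as a whole and no section claims safety within each group, so the pooled figure is the relevant one.
- **The denominator.** The device is first worn at the pre-assessment visit, and dropouts are expected, so the number exposed may exceed 36. The limit then narrows, but not enough to change the conclusion (Step 6).
- **The SAP.** The safety population and the form of the safety tables may be defined in a plan not shown here. Their absence is no fault. The wording of the aim, its criterion and the sample-size argument, however, are all fixed in the protocol.

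Safety oversight also does not rest on a tally alone: adverse events are graded under medical oversight, and monitoring takes place at four points of study completion. That protects participants, but it does not sharpen the estimate of risk.

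**Conclusion.** The point holds as a mismatch between aim and design. About 36 participants cannot establish safety for uncommon harms: no event of a type leaves a per-participant risk of up to about 9.7% open (8.0% one-sided), and one event leaves about 14.5%. This rests on three assumptions: a 95% exact interval, 36 exposed participants, and a per-participant risk over ten supervised sessions. Fewer participants with full exposure would widen the limits, and more exposed participants would narrow them modestly. None of the figures speaks to daily use, which is what the research question asks about.

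The choice of 12 per group is not in error for its stated purpose, and the pilot can usefully estimate how often common events such as near falls occur. What needs correcting is the claim in Aim 1 and the missing statement of what the sample can exclude.

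**What to change.** 1. In Background, Rationale and Goals, item 3, and in Study Procedures, item 2, reword Aim 1 as: *to estimate the frequency of adverse events and near falls during supervised training*.
2. In Study Population, item 3, add that with about 36 exposed participants, zero events of a given type excludes only risks above about 10% (exact two-sided 95% limit), to be restated for the number actually exposed, and that within a group of 12 it excludes only risks above about 26%.
3. State that the safety conclusion will rest on the upper confidence limit for each event type and not on the absence of events. What rate would be acceptable is for the investigators to define.

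The cost is two identical wording changes and a sentence or two. No more patients, visits or measurements are needed. The downside is that the stated safety claim becomes less favourable.

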## Study Population

- 1. \* Provide the maximum number of individuals that
  - May participate in any study interaction or intervention (Including screening, consenting, and study activities)
     AND/OR
  - 2. You obtain any data/specimens about (regardless of identifiability)
  - at VCU and at other sites under the VCU IRB's oversight. See the help text for additional guidance.  $90\,$
- 2. If this is a multi-Center Project, what is the maximum anticipated number of subjects across all sites?

3. \* Provide justification for the sample size by explaining how you arrived at the expected number of participants and why this number is adequate for answering the research questions:

An overarching goal of this pilot study is to obtain estimates of the means and variances of all study measures to facilitate a power analysis for future extramurally funded clinical trials. van Belle proposed that a minimum of 12 observations should be used to calculate confidence intervals based on the t-statistic with n ◆ 1 degrees of freedom.17 This rule is based on the fact that the half-width confidence interval for the mean decreases rapidly up to n = 12, at which point the decrease is less dramatic and the half-width curve begins to asymptotically decrease. Thus, the proposed sample size of 12 per H&Y group (3 groups of H&Y) should be adequate to provide means and variance for planning of future studies.

We also expect to enroll 1 caregiver for each participant enrolled.

We proposed up to 90 participants because we included persons who signed the consent but were ineligible to participate and those that started the protocol but dropped out.

